3. Tell the participant, "I'm going to ask you to tell a story. Have you ever heard the story of Cinderella?" (Make note of answer) "Do you remember much about it? These pictures might remind you of how it goes. Take a look at the pictures and then I'll put the book away, and ask you to tell me the story in your own words." Allow the participant to look through the book (assist with page turning, if needed) and then, if necessary, prompt: "Now tell me as much of the story of Cinderella as you can. You can use any details you know about the story, as well as the pictures you just looked at." Continue until the participant concludes the story or it is clear s/he has finished.
4. Stop web-camera and save video file for later transcription.
5. Administer the PHQ-9. This 9 item scale has high sensitivity and specificity for depression, compared to structured psychiatric interview, in individuals with stroke.

Procedure for Randomizing to fMRI Electrode Placement vs Structural Electrode Placement (Visit 2)

The SLP will take the next sequential sealed envelope (numbered from 1 to 50) from a box, and open it. The card will state "fMRI" or "structural." 25 of the cards will state "fMRI" and 25 will state "structural."

Procedures for Structural and Resting State Functional Connectivity fMRI Examination (Visits 2, 18, 36) (all participants who consent to MRI and have no contraindication)

Date: March 2, 2021

Principal Investigator: [name], MA

Application Number: IRB00089018

The following procedures will be performed:

1. Run the participant on a 10-minute rsfcMRI exam during visits two and immediately after treatment periods 1 and 2: Instruct the participant to lie still in the scanner, eyes open.
2. Run the participant on high-resolution anatomical MRI scans during each of the same visits
Instruct the participant to do lie still during these scans.

Procedures for functional Near-Infrared Spectroscopy (fNIRS) Examination (Visits 2 and follow-up evaluations) (all participants who consent to fNIRS)

The following procedures will be performed:

1. Run the participant on a 10-minute resting fNIRS exam during visits two and at follow-up evaluations: Instruct the participant to sit still, eyes open.
2. Run the participant on task-based fNIRS scans during each of the same visits
Instruct the participant to do sit still and complete the tasks as instructed to the best of their ability.

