In addition to the primary outcome, several secondary analyses will be conducted. We will examine changes in types of naming errors (defined by the PNT) by tDCS treatment group. The Cinderella story will be analyzed by comparing lexical diversity (VOCD) for nouns, verbs, and adjectives; number and types of errors; length and patterns of pauses by treatment group. Pre and post comparisons with both non-aphasic and aphasic speakers from the Aphasia Bank database who share a number of demographic features (e.g., type and severity of aphasia, age, etc.) will also be made. We will also evaluate differences between treatment groups in QOL as measured by the Stroke Impact Scale, mRS, Content Units (CU) and syllables/CU in describing the Cookie Theft picture on the NIH Stroke Scale. At the end of the study, for the interval scale variables, mean change from baseline to immediate post-testing in secondary outcome measures will be reported by treatment group along with the 95% confidence intervals. Treatment comparisons will be made with a paired t- test. For binary variables, the proportion of subjects immediately post-testing will be reported by treatment group along with the 95% confidence intervals.

c. Statistical plan including sample size justification and interim data analysis.

Statistical Analysis

The primary hypothesis is that A-tDCS over a targeted region combined with computer-delivered SALT is associated with greater gains in accuracy in naming pictures, compared to sham combined with the same computer-delivered SALT in post stroke aphasia. To test this hypothesis, we will compare the change in means of outcome measures in the group who received sham versus the group who received tDCS (collapsing across localization subgroups). The primary outcome variable will be change in accuracy of naming untrained items within one week after treatment ends. The null hypothesis is $H_0: \mu_1 = \mu_2$, where μ_1 is the mean change in accuracy of naming untrained items between baseline and one week post-treatment in the A-tDCS group and μ_2 is the mean change in accuracy of naming untrained items between baseline and one week post-treatment in the sham group.

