Since this is a Phase I/II study, the false positive error rate has been relaxed (Schoenfeld, 1980). For a futility design the type I and type II error rates are reversed as compared to a traditional, superiority hypothesis. For the primary analysis, the probability of incorrectly declaring a drug futile is 0.1 (or 10%, type I error is the false negative rate). Given that the active tDCS comes from a distribution with a mean change of the control group (e.g. the treatment is the same as the sham), the probability of incorrectly moving to a Phase III trial is 0.15 (or 15%, type II error is the false positive rate).

For secondary outcomes and safety analyses, no adjustment of Type I error probability will be considered, since they will be treated as exploratory.

Missing Data

Under the ITT principle, all patients who are randomized are included in the analysis. Therefore, missing data, especially in the primary outcome measure, can be problematic. For the primary futility analysis we will impute missing data using multiple imputation (Rubin, 1987) assuming a monotone missing mechanism and missing is at random (MAR). Similar methods will be employed for secondary analyses and secondary outcomes. For safety data (e.g. AEs) no data imputation will be done.

Interim Analysis

No formal interim analyses are planned.

Adjusting for Covariates

The primary analysis will be adjusted for aphasia type, and baseline aphasia severity (AQ), education, time from stroke onset to time of treatment initiation, and number of previous SLP treatment sessions (prior to our study).

Secondary Analyses

In addition to the primary outcome, several secondary analyses will be conducted. We will examine changes in types of naming errors (defined by the PNT) by tDCS treatment group. The Cinderella story will be analyzed by comparing lexical diversity (VOCD) for nouns, verbs and adjectives; number and types of errors; length and patterns of pauses by treatment group. Pre and post comparisons with both non-aphasic and aphasic speakers from the Aphasia Bank database who share a number of demographic features (e.g., type and severity of aphasia, age, etc.) will also be made. We will also evaluate differences between treatment groups in QOL as measured by the Stroke Impact Scale, mRS, Content Units (CU) and syllables/CU in describing the Cookie Theft picture on the NIH Stroke Scale.

At the end of the study, for the interval scale variables, mean change from baseline to immediate

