10. SECONDARY ANALYSES

Secondary analyses will evaluate the effect of A-tDCS vs sham on change in lexical features of discourse, Content Units (CU) and syllables/CU in describing the Cookie Theft picture, HANA, NIH Stroke Scale, SIS, mRS, and PHQ-9.

For continuous measures, the secondary analyses will be adjusted for aphasia type (Anomia, Broca, or other type), baseline aphasia severity (AQ), and age using a linear mixed effects regression to compare treatment groups. The model will include repeated measures of change from baseline to 1, 5, 20 weeks post and visit will be a classification variable with interaction terms for visit*treatment group (SAS PROC MIXED with a REPEATED subcommand).

```
PROC MIXED;
  CLASS SUBJID ARM VISITNUM TYPE;
  MODEL CHANGE= ARM|VISITNUM WABAQ TYPE AGE;
    REPEATED VISITNUM / TYPE= CS SUBJECT=SUBJID R RCORR;
  LSMEANS ARM*VISITNUM/pdiff CL;
RUN;
```

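### Errors in the Cinderella story are compared as a number although the narrative has no fixed length, so the count mixes error rate with amount of speech and the arm contrast can reverse

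*Protocol*

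**What the plan says.** **Outcome.** Protocol 7b lists the discourse measures: "The Cinderella story will be analyzed by comparing lexical diversity (VOCD) for nouns, verbs, and adjectives; number and types of errors". Section 7c repeats the list: "lexical diversity (VOCD) for nouns, verbs and adjectives; number and types of errors; length and patterns of pauses by treatment group". Neither gives a denominator. For interval-scale secondary measures, "mean change from baseline to immediate post-testing in secondary outcome measures will be reported by treatment group", with 95% confidence intervals.

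**Speech sample.** In the protocol's Cinderella Story procedure (section 4a), step 3 has the examiner say "Now tell me as much of the story of Cinderella as you can" and then instructs: "Continue until the participant concludes the story or it is clear s/he has finished". No time limit, word target or truncation rule is given. Step 4 reads "Stop web-camera and save video file for later transcription", so the material for a word count will exist.

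**Contrast within the protocol.** For the other discourse task, the Cookie Theft picture, the same paragraph of 7b names a per-unit measure (syllables per content unit). The naming tests use set lists of items, so a count there has a fixed denominator.

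**SAP.** Section 10 says only: "Secondary analyses will evaluate the effect of A-tDCS vs sham on change in lexical features of discourse". It does not define that term and mentions neither the Cinderella story nor discourse errors. Its model for continuous measures has arm, visit, their interaction, WAB-R AQ, aphasia type and age, with no term for sample length. Section 2 says the SAP will be updated before database lock and that the final version takes precedence over the protocol.

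**Status.** Protocol 7c (Multiplicity) treats secondary outcomes as exploratory. SAP 8.4 calls them supportive of the primary analysis.

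**The concern.** A participant who talks for longer has more chances to make errors. In an open-ended narrative, a change in the number of errors therefore reflects two things: how error-prone the speech is and how much of it there is. If treatment lowers the error rate and lengthens the story, the two pull the count in opposite directions, and its sign cannot be read as benefit or harm.

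At stake is how the discourse results read beside the naming result. If A-tDCS lengthened narratives more than sham, the count could favour sham although active participants made proportionally fewer errors. Leaving the denominator unstated also leaves the choice between count and rate open until the data are seen, and the two can differ in sign.

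**Working it through.** The documents state no figure for this endpoint. Their one power figure belongs to the primary PNT comparison (20 per arm, difference 23, SD 22.2, two-sided alpha 0.05). A noncentral t with 38 df gives 89.1%, which agrees with the stated 89% but has no bearing here. Every word and error input below is an assumption.

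**1. One participant.** Let W be words, r errors per word and E = W × r. Then E1/E0 = (W1/W0) × (r1/r0), and the count rises exactly when that product exceeds 1. Assume a baseline of 100 words with 20 errors.

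- Output doubles: break-even is 20/2 = 10 errors per 100 words. At 12 per 100, E = 200 × 0.12 = 24, up 4 although the rate fell. At 8 per 100, E = 16, down 4.
- Output up 1.5-fold: break-even is 20/1.5 = 13.3 per 100. At 16 per 100, E = 150 × 0.16 = 24, up 4. At 12 per 100, E = 18, down 2.

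**2. Arm contrast.** With equal baselines (mean words W, error rate r0) and output growth factors gA and gS, the contrast in mean count change, active minus sham, is W × (gA·rA − gS·rS). When rA < rS it has the wrong sign if gA/gS > rS/rA.

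Assume median baseline output of 100 words with log SD 0.6, so the mean is 100 × exp(0.6²/2) = 119.7. Assume r0 = 30%, rA = 24% and rS = 27%. The rate contrast is then −3.0 per 100 words throughout.

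Break-even with sham at +25%: gA = 1.25 × 0.27/0.24 = 1.406, about +40%.

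| Growth in words, active vs sham | Count contrast |
|---|---|
| +35% vs +25% | 119.7 × (0.3240 − 0.3375) = −1.6 |
| +50% vs +25% | 119.7 × (0.3600 − 0.3375) = +2.7 |
| +75% vs +25% | 119.7 × (0.4200 − 0.3375) = +9.9 |
| +50% vs +50% | 119.7 × (0.3600 − 0.4050) = −5.4 |

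A positive value makes A-tDCS look worse.

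**3. A second set of inputs.** Both arms start at 100 words and 20 errors per 100. Sham goes to 125 words at 18 per 100: 22.5 errors, change +2.5.

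| Active after treatment | Change in count | Count contrast | Rate contrast per 100 words |
|---|---|---|---|
| 200 words, 14 per 100 | 28 − 20 = +8 | +5.5 | −4.0 |
| 200 words, 12 per 100 | 24 − 20 = +4 | +1.5 | −6.0 |
| 150 words, 14 per 100 | 21 − 20 = +1 | −1.5 | −4.0 |
| 125 words, 16 per 100 | 20 − 20 = 0 | −2.5 | −2.0 |

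The first two rows reverse and the last two do not.

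**4. Sampling variation.** Simulating step 2 with 25 per arm and +50% versus +25% words, the point estimate of the count contrast has the wrong sign in about 77% of trials if output growth varies modestly between participants (log SD 0.2), and in about 87% if it does not vary. Wider variation pulls the share towards one half. Errors per 100 words have the right sign in about 94–96%. With equal growth the count has the right sign in about 89% and 97% under the same two settings. These are signs of point estimates only: at +50% versus +25%, the count significantly favours sham (two-sided 0.05) in only about 6–20% of trials, for log SD of growth from 0.5 down to 0.

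**The case against.** **The protocol names topics, not a scoring rule.** It gives no error taxonomy for the story and no direction of benefit, and the recordings allow a rate to be derived. This stands in part. A reader might infer that the plan commits to scoring a higher count as a worsening, and the text does not go that far. But a number is the only measure written down, and the same paragraph supplies a per-unit measure for Cookie Theft.

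**The SAP takes precedence and does not name discourse errors.** True, so it is unclear whether the measure survives as a pre-specified outcome, and section 10 contains no error wording to replace. That leaves the gap open, because the SAP term is undefined and the protocol holds the only description.

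**Nothing predicts longer narratives under A-tDCS.** This stands. The treatment is picture–word verification by button press, the objective is naming, and protocol section 9 allows that gains may not generalise. The reversals in the arm contrast computed above all need output to grow more under A-tDCS than under sham.

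**A stronger reading goes too far.** A reader might infer that any participant who recovers and says more will score as worse. Step 1 shows otherwise: the count rises only when output grows by a larger factor than the error rate falls.

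**The reach is small.** This also stands. Lexical diversity, content units and syllables per content unit are planned alongside, and the Phase III decision in protocol 7c rests on the primary hypothesis test.

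**Conclusion.** The point holds as a defect in how one outcome is defined. As written, the error comparison confounds error rate with length of narrative, and neither document corrects for it. A participant's count can rise while the error rate falls, and the arm contrast can take the wrong sign.

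How often that would happen cannot be settled from the documents. It depends on whether gA/gS exceeds rS/rA, and both ratios are assumed here. The documents do not support the inference that a reversal is likely, or that the discourse evidence as a whole would contradict the PNT result. The primary analysis, its power and the Phase III decision are unaffected. The change is worth making because it is a better measure at almost no cost, not because a reversal is expected.

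**What to change.** In protocol 7b and 7c, replace the number of errors in the Cinderella story with errors per 100 words produced, in total and for each error type. Alternatively, analyse the count in a count model with log(total words) as offset. Report total words by arm as a separate outcome. A participant with no words at a visit has neither a defined rate nor a defined offset, so report the number of such participants by arm at each visit.

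In SAP section 10, define the discourse term and, if errors are kept, include this measure in the definition. The update that SAP section 2 already foresees before database lock is the place to do it, before the code is broken.

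The cost is wording only: the recordings are already kept for transcription, and the transcripts yield word counts. The small downside is that rates from very short samples are noisy. The offset model handles this by giving short samples less weight.

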After informed consent is received, a neurological examination will be performed and multiple screening assessments will be conducted including a tDCS and MRI safety screening (see below). If the participant passes the initial screening portion, speech and language diagnostic testing will be conducted during the same visit (Visit 1). During the next visit (Visit 2), participants will undergo a second baseline assessment of naming ability and assessment of connected speech. On that visit, participants who have no contraindication for MRI will be randomized to (1) fMRI electrode placement or (2) structural electrode placement. All participants who have no contraindication will have structural and rsfcMRI. Those randomized to fMRI electrode placement will also participate in the naming paradigm. Those who agree will also undergo fNIRS. The third visit will include electrode positioning and tDCS treatment administration. Participants will receive 15 sessions (Visits 3-17) of tDCS treatment administration. At the beginning of Visit 3, eligible participants will be randomized to receive either A-tDCS (1 mA) or sham-tDCS (placebo) for 15 sessions (20-minutes per each 45-minute behavioral treatment session) over the course of three weeks. A computer-delivered naming treatment will be coupled with the stimulation. The computer-delivered treatment task will be 45-minutes in total length, so that it will commence at the same time as the tDCS administration and continue for another 25-minutes after the tDCS has ceased.

c. Blinding, including justification for blinding or not blinding the trial, if applicable.

Randomization and Blinding

The study is to be conducted in a double-blind manner. The subjects, the site investigators, and the clinical staff involved in this study will not know the treatment assignment. Select members of the statistical and Data Management Center will be partially blinded, i.e., they will know the treatment group assignment as A or B, but not whether the patient receives active tDCS or sham. The study statistician and the DSMB will have a sealed envelope with the treatment group identifiers. This envelope would only be opened if the study statistician is directed to open it by the DSMB or at the end of the futility study.

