The primary analysis will compare change in accuracy of naming untrained items between groups (A-tDCS versus sham) in a two-sample *t*-test for the Intent-to-treat sample. For participants who do not complete the Week 1 post-treatment assessment, the post-treatment value will be imputed using a multiple imputation approach assuming a monotone missing mechanism and missing is at random (MAR). As a sensitivity analysis, the primary outcome analysis will be repeated using all available follow-up data (without explicit imputation) in a mixed effects model of the change from baseline in naming accuracy adjusted for baseline (with Week 1, 5, or 20 as a categorical variable and a random effect for subject). Similar analyses will be done for the change in accuracy of trained items.

If we accept the null hypothesis, then tDCS is considered clearly ineffective (in improving anomia in stroke patients) and will not be considered for further study. If we reject the null hypothesis, we would consider undertaking a Phase III study of tDCS.

Sample Size Determination

We expect to enroll 50 participants over 4 years, and expect 40-45 will complete the study. We predict no difficulty recruiting at least 10-15 participants with aphasia each year after subacute stroke, as the PI has

Date: March 2, 2021

Principal Investigator: [name], MA

Application Number: IRB00089018

recruited an average of 53 aphasic patients due to acute left hemisphere ischemic stroke each year in her previous studies of aphasia recovery. If sample size in each group is 20, (a total sample size of 40), we will have 89% power to detect a difference in means of 23 (the difference between a A-tDCS mean change in accuracy, μ_1 , of 33 and a sham mean change in accuracy, μ_2 , of 10) assuming that the standard deviation of change for both groups is 22.2 using a two group *t*-test with a two-sided alpha of 0.05. These mean changes for tDCS and sham and standard deviation of change are based on the one published sham-controlled study of tDCS combined with SALT in subacute stroke.

Multiplicity

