2. STATISTICAL ANALYSIS PLAN AND STATISTICAL REPORTS

This document provides the details of the statistical analyses planned for the trial. Prior to locking the database and breaking the code, this Statistical Analysis Plan (SAP) will be updated. The final SAP will define all “pre-specified, pre-planned analyses” and will trump the protocol.

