4. STUDY DESIGN AND OBJECTIVES

Subjects will be randomized 1:1 to A-tDCS or S-tDCS, with the goal of having 50 randomized subjects for whom the PNT was collected at 1 week post-treatment. This study design will allow us to assess whether A-tDCS over targeted region coupled with computer-delivered SALT is associated with greater gains in accuracy in naming pictures, compared to sham combined with the same computer-delivered SALT in post stroke aphasia.

The primary objective of the study is to determine whether A-tDCS coupled with SALT will improve naming performance of participants with post stroke aphasia more effectively than SALT alone (i.e., the sham condition).

Planned enrollment duration: approximately 4 years (1.04 patients /month)

Duration of treatment phase: 3 weeks

Duration of follow-up in post-treatment Phase: 20 week post treatment (i.e. 23 weeks from baseline)

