8.2 Statistical Hypotheses

The Primary Hypothesis 1a: A-tDCS over a targeted region coupled with computer-delivered SALT is associated with greater gains in accuracy in naming pictures, compared to sham coupled with the same computer-delivered SALT in post stroke aphasia. To test this hypothesis, we will compare the change in means of outcome measures in the group who received sham versus the group who received tDCS. The primary outcome variable will be change in accuracy of naming untrained items within one week after treatment ends. The null hypothesis is $H_0: \mu_1 = \mu_2$, where μ_1 is the mean change in accuracy of naming untrained items (PNT correct) between baseline and 1 week post-treatment in the A-tDCS group and μ_2 is the mean change in the sham group. The primary analysis will compare change between groups (A-tDCS versus S-tDCS) using multiple regression and will be adjusted for aphasia type (Anomia, Broca, or other type), baseline aphasia severity (AQ), and age. The primary analysis will be performed using both the Completers and Modified Intent-to-treat Samples. If these two analyses are not consistent, then the trial findings will be interpreted with caution.

Sensitivity analyses will be done for the change in accuracy of trained items using the same approach. Naming errors will also be analyzed and categorized as semantic related, semantic unrelated, real words related phonologically, non-words related phonologically, mixed semantic/phonological, abstruse neologisms, and no response. Additional sensitivity analyses will adjust for education and time from stroke onset to time of treatment initiation in addition to the covariates included in the primary model.

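### A non-significant primary test is to be read as proof that tDCS does not work, the SAP does not replace that rule, and a leftover 15% futility error rate contradicts the planned test

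*Protocol*

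**What the plan says.** **The decision rule.** Protocol section 2 (Primary Analyses) and section 7c (Statistical Analysis) set the null hypothesis as equal mean change in naming untrained items. Both then say: "If we accept the null hypothesis, then tDCS is considered clearly ineffective (in improving anomia in stroke patients"), and that tDCS will not be pursued. If the null is rejected, a Phase III study would be considered. Sample size is justified by a two-group t-test at two-sided 0.05 with 20 per group: "we will have 89% power to detect a difference in means of 23".

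**The futility wording.** Protocol section 7c (Multiplicity) describes a futility design with reversed error rates: 10% for wrongly declaring futility, and, if tDCS equals sham, "the probability of incorrectly moving to a Phase III trial is 0.15 (or 15%, type II error is the false positive rate"). Section 7c (Missing Data) says "For the primary futility analysis we will impute missing data using multiple imputation". Section 4c says the unblinding envelope is opened only if the statistician is "directed to open it by the DSMB or at the end of the futility study". No futility null or margin is stated anywhere.

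**The SAP.** Section 2 says the final SAP will define the pre-planned analyses "and will trump the protocol". Section 8.2 keeps the equality null and compares groups "using multiple regression and will be adjusted for aphasia type (Anomia, Broca, or other type), baseline aphasia severity (AQ), and age". Section 8.4 sets two-sided 0.05 for the primary analysis. The SAP omits both the protocol's decision rule and the futility rates. Its only rule of interpretation is to be cautious if the Completers and modified ITT analyses disagree. Section 4 aims for a larger sample than the power statement uses, "with the goal of having 50 randomized subjects for whom the PNT was collected at 1 week post-treatment".

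**The concern.** A test of equality that does not reject says that the data are compatible with no difference. It does not say that they are incompatible with a worthwhile one. To call a treatment ineffective, the interval for the effect must exclude every difference that would matter, and neither document names such a difference. The 89% power gives protection only at a true gain of 23, a figure taken from one earlier sham-controlled study.

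At stake is how a null primary result is read and whether tDCS in subacute aphasia is studied again. Under the rule, a result whose 95% interval still contains the design difference would count as showing no effect.

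The futility paragraph is a separate and smaller problem. A reader who took it at face value would think the chance of a false step to Phase III is 15%.

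**Working it through.** **Inputs.** Difference 23 (33 versus 10), SD of change 22.2, 20 per group, two-sided 0.05 (Protocol 7c; SAP 8.3 and 8.4). The SAP section 4 target of 50 with 1:1 allocation gives 25 per group. Gains of 10 and 11.5 (half of 23) are illustrations only.

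**Step 1. Reproduce the stated power.** SE = 22.2 × √(2/20) = 7.02. Noncentrality = 23/7.02 = 3.28 on 38 df, with critical t = 2.024. Power = 89.1%, which matches the stated 89%. The figure therefore belongs to the two-sided 0.05 superiority test.

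**Step 2. How often the label would be applied.** P(not reject) = P(|T| < critical t), with T noncentral t and noncentrality (true gain)/SE. For 25 per group, SE = 22.2 × √(2/25) = 6.28 and critical t = 2.011 on 48 df.

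| True gain | 20 per group | 25 per group |
|---|---|---|
| 23 | 10.9% | 5.2% |
| 11.5 | 64.2% | 56.6% |
| 10 | 71.6% | 65.5% |

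**Step 3. Results labelled ineffective whose interval contains 23.** The expected 95% CI half-width is 2.024 × 7.02 = 14.21 (20 per group) or 2.011 × 6.28 = 12.62 (25 per group). A result is non-significant below the half-width, and its interval contains 23 above 23 minus the half-width.
- 20 per group: observed advantages from 23 − 14.21 = 8.79 to 14.21.
- 25 per group: observed advantages from 23 − 12.62 = 10.38 to 12.62.

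In 1,000,000 simulated trials at a true gain of 23, 8.5 of the 10.9 percentage points of false labels (3.0 of 5.2 with 25 per group) are of this kind.

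**Step 4. Covariate adjustment.** The SAP's primary model adjusts for aphasia type, AQ and age, and the documents give no residual SD. With an assumed residual SD of 18, the label falls on a true gain of 10 in 59.8% (51.4% with 25 per group) and on 23 in 2.4% (0.7%). The band in step 3 closes once the half-width is below 23/2 = 11.5:
- SD below 11.5/(2.024 × √(2/20)) = 17.96 with 20 per group;
- SD below 11.5/(2.011 × √(2/25)) = 20.22 with 25 per group.

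In variance explained, these are 1 − (17.96/22.2)² = 35% and 1 − (20.22/22.2)² = 17%.

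**Step 5. The 15%.** If tDCS equals sham, a two-sided 0.05 test rejects in 5% of trials, 2.5% in favour of tDCS. A false-go rate of 15% would need a one-sided 0.15 test (power 98.7% at 23 with 20 per group) or a two-sided 0.15 test (96.3%). Neither agrees with the stated 89%. The accompanying 10% is close to the planned test's 10.9% type II error with 20 per group, so the clear conflict is the 15%.

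**The case against.** The strongest reply is that the SAP governs and has already moved on. Section 8.4 fixes two-sided 0.05, so the 15% has no force, and section 8.2 restates the null without the disputed sentence, perhaps deliberately. The first part stands: the 15% is leftover protocol text. The second does not settle the matter. For alpha the SAP puts something in place of the protocol text; for the decision rule it puts nothing.

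The SAP does plan an active-versus-sham 95% interval at 1, 5 and 20 weeks (section 8.5), so readers would see one. It comes from the mixed-model sensitivity analysis, however, and no rule ties the conclusion to it.

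The large rates in steps 2 and 3 are for an unadjusted test that the SAP no longer uses. This stands as a limit on the size. At a residual SD of 18 and a true gain of 23, results labelled ineffective with 23 inside the interval fall to about 1.0% of trials (0.07% with 25 per group). A gain of 10 would still be labelled ineffective in more than half.

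Finally, the documents state a go/no-go view and do not say how a null result would be published. That is fair. The wording is still a scientific claim and goes beyond a decision to stop.

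**Conclusion.** The concern holds. The protocol's rule draws a conclusion of no effect that a non-significant test of equality cannot support, and the SAP leaves it unreplaced. The mislabelling rate is 11% (5% with 25 per arm) at the design gain of 23 and about two thirds or more at a gain of 10. These figures assume an SD of 22.2 and no covariate adjustment. Adjustment would reduce them by an amount that cannot be known from the documents. The choice of 10 and 11.5 is illustrative, since no smallest worthwhile difference is given.

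The 15% false-go rate cannot belong to the planned test, whose rate is 5% (2.5% in favour of tDCS), and should be removed as a remnant. The point should be fixed before the final SAP. It affects interpretation only.

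**What to change.** **Protocol.** Delete the sentence equating acceptance of the null with ineffectiveness (sections 2 and 7c), the futility error-rate paragraph (7c, Multiplicity), and the word futility in sections 4c and 7c (Missing Data).

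**SAP.** Keep two-sided 0.05. State that a non-significant result is not evidence of no effect and that the result is read from the estimate and 95% CI for A-tDCS minus sham at 1 week, in this order:
1. Lower limit above 0: consider Phase III.
2. Otherwise, upper limit below a pre-specified and justified smallest worthwhile difference: that difference is ruled out.
3. Otherwise: inconclusive.

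The sponsor has to supply and justify the difference in step 2. If 23 is used, the conclusion may say only that an effect as large as 23 is ruled out. Step 2 would also be reached in 43% of trials at a true gain of 10 (51% with 25 per arm).

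**Cost.** A few sentences, and some null results become inconclusive. With SD 22.2 and 23 in step 2, this is 8% of trials under no effect and 28% at a true gain of 10 with 20 per arm (3% and 14.5% with 25). A smaller difference costs more: with an illustrative 11.5, about 62% (54%) of trials under no effect would be inconclusive.
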